
For those age 16 or 17, parent/guardian consent will be obtained from at least one parent. Parent/guardian consent will be attempted to be obtained from both parents unless one parent is deceased, unknown, incompetent or not reasonably available due to travel or work. Permission will be obtained from someone other than a parent only when that person is a legal guardian of the potential participant. Assent will be obtained and documented from all participants that meet criteria and are willing to consent that are age 16 or 17. Documentation will be obtained by child signing Assent Form (ink or electronic signature if conducted via video conference), along with research staff personnel obtaining consent (ink or electronic signature if conducted via video conference).

Randomization and Double-Blind: Participants that meet criteria for entry into the study based on the online screen and the clinical interview will be randomized to active NAC (low dose versus high dose), versus PBO. We will implement an adaptive randomization procedure similar to stratification called minimization. The purpose of the procedure is to ensure that the 3 groups are similar with respect to key demographic and clinical variables such as age, depression severity, NSSI severity and medication use. These variables will be shared by the research coordinator in a de-identified file with the study statistician, who will use the information to complete the randomization procedure. She will then share the group assignment with IDS. All participants, family members, and the entire research team will be blinded to active NAC versus PBO assignment.

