Clinical Assessment-Assessment of General Psychopathology and Demographic Information: To describe our sample and to determine criteria for ineligibility, we will screen for the presence of Diagnostic and Statistical Manual of Mental Disorders-5th edition (DSM-5) (American Psychiatric Association 2013a) psychiatric diagnoses (American Psychiatric Association 2013b). We will conduct a clinical interview with the participant using the Mini International Neuropsychiatric Interview (MINI; (D. V. Sheehan et al. 1997) for all participants. Assessment interviews will be conducted by trained research team members, directly after the consent process. Consent and baseline clinical assessment are expected to take 2 to 3 hours to complete. The Wechsler Abbreviated Scale for Intelligence-II (IQ; (Wechsler 2011) will be used to estimate intellectual functioning, to be completed on Day 1 or 28. The Edinburgh Handedness Inventory (Oldfield 1971) will be used to determine handedness, which will be incorporated into the analysis. We will monitor the groups' equality with respect to socioeconomic status using the Hollingshead Four Factor Index of Social Status (Hollingshead 1975) after collecting demographic information with a self-report form. We will also collect past antidepressant medication trials with an Anti-Depressant Medication form, other psychotropic medications with Any Psychotropic Medications form and treatment history with Treatment History form, all via REDCap. The Child Trauma Questionnaire (CTQ) (Bernstein D.P & Fink 1998) includes 6 questions about past trauma and 7 about recent trauma. Depression severity will be measured using the Beck Depression Inventory-II (BDI-II; (Osman et al. 2004) and the Patient Health Questionnaire (PHQ-9) (Kroenke et al. 2001). We will also administer the medication side effects checklist to assess baseline symptom overlap with responses to this checklist at later stages of the study. Assessment of NSSI and Suicidality. We will use the Self-Injurious Thoughts and Behaviors Interview (SITBI) (Nock et al. 2007) to elicit NSSI history (age of onset, total past episodes, episode frequency, reasons for NSSI, thoughts about NSSI, and other information) and use the Inventory of Statements about Self-Injury (ISAS-Lifetime) to assess the functions and frequency of behaviors of NSSI (Klonsky & Glenn 2009). We will use the Alexian Brothers Urge to Self-Injure (ABUSI) scale to assess urges to engage in NSSI. We will use the Beck Scale for Suicidal Ideation (BSS; (Beck, Kovacs, and Weissman 1979) to assess current suicidal ideation, including active suicidal desire, specific suicide plans, and passive suicidal desire. To retrospectively assess mood before, during and after NSSI events we will use the Deliberate Self Harm Questionnaire, Part III Mood (DSHQ-M). We will use the Distress Tolerance Scale (DTS) to assess emotional distress tolerance (Simons & Gaher 2005). We will use the one-question Cash Choice Task as a delay discounting measure to further assess executive functioning (Wulfert et al., 2002). Finally we will use the Side Effect Checklist to assess baseline symptoms on this form at Day 0, before participant takes study drug/placebo. The demographic history form, antidepressant medication form, any psychotropic medications form, treatment history form, PHQ-9, ISAS-SLV, ISAS-Lifetime, ABUSI, DTS, SITBI, Cash Choice Task, Side Effect Checklist, and

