are similar with respect age, NSSI severity, and medication use. Specifically, the minimization procedure will balance age groups <19 vs. 19+ years, NSSI severity category mild vs. moderate vs. severe; and anti-depressant use vs. no anti-depressant use. Following the evaluation, the study coordinator will share numerical values for these variables along with the subject ID number through a secure system (Box Secure Storage) with the study statistician, [name]. [name] will use participant information to assign a blinded randomization group (A, B, or C) using the minimization procedure.

The study statistician will then pass the blinded group assignment to IDS. Before the first participant is randomized, IDS will randomly assign “NAC high” “NAC low” and “PBO” to the letters A, B, and C; this assignment (of treatment name to treatment letter) will not be communicated to anyone outside of IDS until the study is complete and the study team is ready to break the blind. Randomization will occur after Visit 1 (Day 0), when it is confirmed all eligibility criteria are met and before Visit 2 (Day 1), with a maximum 30 day window between them.

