9.2 Sample Size and Randomization

The sample size (n=12 per group) was selected based on calculations on biosignature data from the oral NAC pilot study in adults with either Parkinson's disease (PD; n=5) or healthy controls (HC; n=3). Using variability estimates from this study, we found that with groups of 11 (assuming one drop-out per group), we would have 80% power to show a significant ($\alpha=0.0167$, Bonferroni corrected for 3 pairwise comparisons) effect of NAC high vs. NAC low vs. PBO on our primary outcome of brain GSH if the variability is similar to healthy controls seen in our pilot work (detectable mean group difference in pre-dose to post-dose percent change of 2.95%, expected mean group difference ~4.83%). The data collected in the R61 will serve to provide the variability information needed to design a future, confirmatory clinical trial.

Treatment Assignment Procedures

Randomization and Double-Blind: Participants who meet criteria for entry into the study (based on the online screen and the clinical interview) and who provide consent will be randomized to active NAC low dose versus NAC high dose versus PBO (1:1:1). We will implement an adaptive randomization procedure called minimization. The purpose of the procedure is to ensure that the 3 groups are similar with respect to key demographic and clinical variables such as age, NSSI severity and medication use. See Section 6.2.2 for a complete description of the randomization procedure.

All participants, family members, and study staff (including the study statistician) will be blinded to treatment assignment. The research pharmacy, IDS, will be the only unblinded entity. See Section 6.2.2 for a complete description of the blinding (and unblinding) procedures.

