9.6 Data Analyses

To address the study objectives, we will quantify the within-person percent change in proposed primary biological signature: brain GSH. We will fit a general linear model with brain GSH as dependent variable with group (NAC high vs NAC low vs PBO) as the predictor variable of interest. Since we apply a minimization procedure to ensure that groups are similar on key demographic and baseline clinical variables (age, baseline NSSI severity, presence of concurrent psychotropic medication), as is typically done in a large clinical trial we will not include covariates. Should the primary outcome values be highly skewed, we will use non-parametric tests instead to compare groups. We will use the standardized Wilcoxon test statistic with the Dwass, Steel, Critchlow-Fligner (DSCF) multiple comparison analysis. This analysis takes each pair of groups, one pair at a time (high NAC vs. low NAC; high NAC vs. placebo; low NAC vs. placebo), computes a Wilcoxon test statistic to compare the two groups in that pair, and obtains a pvalue that is analogous to Tukey's control of family-wise Type I error (the test statistic is scaled to Tukey's studentized range distribution) (Hollander and Wolfe, 1999). This analysis to compare the 3 treatment groups on the primary outcome will adjust type I error using Tukey's procedure for the 3 pairwise comparisons among the 3 groups. Tukey's procedure is less conservative than the Bonferroni adjustment used in the sample size/power

calculation, hence we expect slightly higher power than planned. We will quantify the effect size of each group's change to determine next steps with the research.

To assess the robustness of our conclusions about the primary outcome to participants whose medical profile changes during the course of active treatment in our study, we will conduct sensitivity analyses. For example, if participant(s) need to have a change in their non-study medications during our study, they will remain in the study but the changes in medications will be noted in the study database. We will repeat our primary analysis excluding such people to see if our conclusions remain the same. We note, however, that this analysis is not protected from bias by the randomization.

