To address the secondary study objectives of exploring additional potential biosignatures, we will fit similar general linear models with each of the additional outcomes (brain Glu, blood GSH/GSSG, antioxidant protein levels, GABA concentrations, amygdala-insula functional connectivity) as dependent variables, with group (NAC high vs NAC low vs PBO) as the predictor variable of interest, again without including covariates to preserve power. These secondary analyses will use Holm's step-down Bonferroni type I error correction to adjust for both multiple comparisons among groups and multiple testing across the several secondary outcomes.

Data analysis: To address the secondary outcome of NAC PK, NAC and GSH concentration-time data will initially be analyzed by non-compartmental methods. WinNonLin Phoenix (Pharsight®) will be used to calculate the partial NAC area under the curve (AUC_0-2h) using the linear trapezoidal rule and maximum concentration (Cmax). The AUC_0-2h and Cmax for GSH will also be calculated. Descriptive statistics of the PK parameters will be determined. Drug concentrations and other PK variables will be correlated with degree of change in biological signatures.

To address the secondary objective of describing the tolerability of oral NAC at the proposed study doses, we will quantify rates of side effects and other adverse events and compare rates between groups using Poisson, survival, or other rate-based models as appropriate for each event type.

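### Section 9.6 leaves the minimisation factors out of the primary and secondary linear models; if those factors predict the outcome, the tests are conservative and less powerful than an adjusted analysis

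*Combined protocol and SAP*

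**What the plan says.** Section 6.2.2 (Randomization) gives the working definition of the allocation: the procedure will "balance age groups <19 vs. 19+ years, NSSI severity category mild vs. moderate vs. severe; and anti-depressant use vs. no anti-depressant use". Section 9.6 then defines the primary outcome as a change score ("we will quantify the within-person percent change in proposed primary biological signature: brain GSH") and fits a general linear model with treatment group as the only predictor. Its reason is the balance that minimisation creates: "as is typically done in a large clinical trial we will not include covariates". For the secondary biomarker models it omits covariates once more, this time for a different reason: "again without including covariates to preserve power". The one sensitivity analysis described excludes participants whose non-study medication changes; none adjusts for the allocation factors.

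The factor list is not the same everywhere. Section 6.2.2 balances antidepressant use. Section 9.6 names concurrent psychotropic medication instead, which is a wider class. Section 4.3 lists "key demographic and clinical variables such as age, depression severity, NSSI severity and medication use", which adds a fourth variable.

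Section 6.2.2 (Clinical Assessment) also says that the Edinburgh inventory "will be used to determine handedness, which will be incorporated into the analysis", while no model in section 9.6 contains handedness.

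**The concern.** When allocation is forced to balance a factor, that factor's contribution to the outcome largely cancels out of the difference between arms. A group-only model still counts it in the residual variance. If the factor is prognostic, the reported standard error is larger than the true sampling variability of the treatment difference, so confidence intervals are too wide and the test rejects less often than its stated level. Good balance is therefore an argument for adjustment. The appeal to large-trial practice does not fit 36 participants, and omitting the factors protects power only when they explain almost nothing.

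At stake is precision in the primary GSH comparison and in the secondary biomarker comparisons. The latter have no power statement and are also subject to a Holm correction across outcomes and group pairs. Separately, the handedness sentence leaves room to add a covariate after the data are seen.

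**Working it through.** **Inputs from the documents.** 12 randomised and 11 analysed per group, 80% power, detectable difference 2.95 points, expected difference about 4.83 points, alpha 0.0167 (section 9.2); allocation 1:1:1; three factors with 2, 3 and 2 levels (section 6.2.2); Tukey adjustment for three pairwise comparisons (section 9.6). Adjustment uses (2 − 1) + (3 − 1) + (2 − 1) = 4 degrees of freedom.

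**Plan's own figures.** 0.05 / 3 = 0.0167 reproduces. The 80% cannot be checked independently because no SD is given. Solving n = 11, difference 2.95, two-sided alpha 0.0167 and power 0.80 for the SD gives 1.98 (noncentral t, 20 df), 2.04 (30 df) or 2.14 (normal approximation). The calculations below use 1.983. The resulting standard error is 1.983 × √(2/11) = 0.846 points.

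**Assumptions.** The documents do not give R2, the share of variance in GSH percent change explained by the factors, so it is varied. Also assumed: equal frequencies of factor levels, equal variance share per factor, minimisation assignment probability 1.0 or 0.8 (not stated), dropout at random, and a 5% family-wise level.

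**Approximation under perfect balance.** The ratio of model SE to true SE is 1/√(1 − R2), and the two-sided level of a single 5% test is 2[1 − Φ(1.96/√(1 − R2))]:
- R2 = 0.1: ratio 1.054, level 3.9%
- R2 = 0.2: ratio 1.118, level 2.8%
- R2 = 0.3: ratio 1.195, level 1.9%

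**Simulation.** 20,000 trials per setting, 36 minimised with probability 1.0, 33 analysed, Tukey at 5%. Power is for high dose against placebo at 2.95 points. Arrows run from group-only to factor-adjusted.

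| R2 | Group-only: mean model SE / true SD of estimate | Family-wise error | Power |
|---|---|---|---|
| 0 | 0.841 / 0.849 = 0.99 | 5.1% → 5.0% | 84.1% → 82.4% |
| 0.05 | 0.843 / 0.828 = 1.02 | 4.6% → 5.0% | 84.0% → 83.9% |
| 0.1 | 0.844 / 0.814 = 1.04 | 3.9% → 5.1% | 84.3% → 86.0% |
| 0.2 | 0.846 / 0.773 = 1.09 | 2.9% → 4.9% | 85.1% → 90.2% |
| 0.3 | 0.849 / 0.739 = 1.15 | 2.0% → 5.0% | 86.1% → 93.7% |

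Monte Carlo error on the 5% rates is about 0.15 points.

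With assignment probability 0.8 the pattern is the same: at R2 = 0.3 family-wise error goes from 2.3% to 4.9% and power from 85.9% to 93.5%; at R2 = 0 power goes from 83.7% to 81.2%. A separate simulation with all 36 analysed gave group-only family-wise errors of 3.5%, 2.8% and 2.0% at R2 = 0.1, 0.2 and 0.3.

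**More attrition.** Section 4.3 allows up to 46 enrolled to obtain 36 completers, and section 9.3 analyses only those with both scans and blood draws. Minimising 46 and analysing a random 36 loosens the balance. In that setting the group-only SE at R2 = 0.3 is about 12% too wide, and power at R2 = 0.2 goes from 87–89% to 91–92%. The direction holds and the SE error shrinks.

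**The case against.** The strongest reply is that everything depends on an R2 the documents do not report. The outcome is a within-person percent change, so stable differences between people are already partly removed, and nothing in the documents shows that age band, NSSI category or antidepressant use predicts change over four weeks. At R2 = 0 the group-only analysis is correct and adjustment costs 1.7 to 2.5 points of power; below about R2 = 0.05 the power rationale in section 9.6 is right. This stands, and it makes the point conditional. It does not rescue the plan's reasoning: the sponsor chose these variables as important enough to balance on, and the possible loss is small beside the gain if they matter moderately.

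Three stronger readings are tempting and are not supported:
- A reader might infer that the trial is underpowered. At 2.95 points, group-only power under Tukey is about 84% or more in every setting, and at 4.83 points it is about 99.8%. These figures do rest on an SD back-solved from the plan's own 80%, which depends on variability resembling that of three healthy controls in the pilot.
- A reader might infer that a positive finding would be unsafe. The error is conservative, so a significant result stands.
- A reader might infer that every analysis omits the factors. The tolerability models and PK correlations state no covariate policy, and the rank-based fallback for skewed data takes no covariates.

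Handedness is not an allocation factor. That conflict is a separate matter of wording and says nothing about the standard error.

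**Conclusion.** The concern holds in conditional form. If the minimisation factors predict the outcome, the group-only linear models overstate the standard error, test below their nominal level and have less power than models containing the factors. For the primary outcome the SE is roughly 4%, 9% and 15% too wide at R2 = 0.1, 0.2 and 0.3 with 33 analysed, and less with heavier attrition. The power forgone at 2.95 points is 90.2 − 85.1 = 5.1 points at R2 = 0.2 and 93.7 − 86.1 = 7.6 points at R2 = 0.3. The sizes rest on the assumed R2, the back-solved SD and the simulated minimisation settings; the direction does not depend on the last two.

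The prespecified unadjusted analysis is valid, only possibly inefficient. The two reasons given for it are weak whatever R2 turns out to be: balance argues for adjustment, and power is preserved only when R2 is near zero. The inconsistent factor list and the handedness conflict are present in the text regardless of R2.

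**What to change.** 1. Reconcile the factor list in sections 4.3, 6.2.2 and 9.6 to the variables actually used in the minimisation, settling antidepressant use against psychotropic medication and whether depression severity is included.
2. In section 9.6, fit the primary and secondary linear models with group plus those factors, coded as for allocation (4 degrees of freedom under section 6.2.2; more if a factor is added). Use Tukey-adjusted differences between adjusted means for the primary outcome and Holm for the secondaries.
3. Keep the unadjusted model as a sensitivity analysis.
4. Remove the large-trial and power-preservation rationales.
5. Reconcile the handedness sentence in section 6.2.2 with section 9.6 before unblinding, either by deleting it or by naming the analysis it refers to.

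This is a cheap improvement: SAP wording, no new data, and four degrees of freedom. The downside is about 2 points of power if the factors are not prognostic. Even then, simulated adjusted power under Tukey at 2.95 points is 81.2% to 82.4%, above the planned 80%. The rank-based fallback would remain unadjusted, and section 9.6 should say so.

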9. STATISTICAL CONSIDERATIONS

9.1 General Design Issues

The goals of this study are to test whether significant change can be found in candidate biological signatures after 4 weeks of oral NAC. Three groups are used to compare pre-post treatment changes in those who received NAC 5400mg/day, 3600mg/day, or PBO.

Primary Hypothesis:

- 1) NAC high dose and/or NAC low dose (but not PBO) will increase cortical GSH by at least 5%

Secondary Hypotheses:

- 1) NAC high dose and/or NAC low dose (but not PBO) will decrease cortical GLU by at least 5%
- 2) NAC high dose and/or NAC low dose (but not PBO) will increase blood GSH/GSSG by at least 50%
- 3) NAC concentrations (using data from both dose groups) will be correlated with clinical and neuroimaging outcomes.
- 4) NAC high dose and/or NAC low dose (but not PBO) will increase resting-state functional connectivity between amygdala and insula
- 5) NAC high dose and/or NAC low dose (but not PBO) will increase ACC GABA.
- 6) NAC high dose and/or NAC low dose (but not PBO) will increase antioxidant protein levels (catalase and heme oxygenase-1 [HO-1]).
- 7) Higher-dose NAC will show larger changes in all of the biological signatures listed above compared to lower-dose NAC
- 8) While both NAC doses will be acceptable to most patients, lower-dose NAC will be better tolerated than higher-dose NAC.

Primary outcome measures:

- 1) GSH concentration in ACC

Secondary outcome measures:

- 1) Blood GSH/GSSG (the reduced-to-oxidized GSH ratio in blood)
- 2) Glu concentrations in ACC
- 3) Tolerability of NAC as measured using a side effects checklist
- 4) Pharmacokinetic analysis of NAC and its metabolites, CYS and GSH
- 5) Antioxidant protein levels (catalase and heme oxygenase-1 [HO-1]) for which

previous studies have shown increases following NAC treatment.

- 6) GABA concentrations in the ACC. Our pilot study found a significant increase in GABA levels after 28 days of oral NAC (6000 mg/day) ([name] et al. 2018).
- 7) Functional connectivity between amygdala and insula. Our pilot study showed that after treatment with oral NAC (3600 mg/day), participants with NSSI showed an increase in amygdala functional connectivity in a cluster that included the bilateral insula.

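### Section 9.6: single-step Tukey is valid, but with exactly three groups its step-down version is a cheap gain in power for low dose versus placebo and high versus low under a graded dose response

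*Combined protocol and SAP*

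**What the plan says.** Section 9.6 fits a linear model to within-person percent change in brain GSH with group as the only predictor. It controls type I error by Tukey's "procedure for the 3 pairwise comparisons among the 3 groups". If the outcome is highly skewed, the fallback is: "We will use the standardized Wilcoxon test statistic with the Dwass, Steel, Critchlow-Fligner (DSCF) multiple comparison analysis".

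The reason given for Tukey is power: "Tukey's procedure is less conservative than the Bonferroni adjustment used in the sample size/power" calculation, so slightly more power than planned is expected. Section 9.2 sized the trial at a significance level of 0.0167, "Bonferroni corrected for 3 pairwise comparisons", and states that "with groups of 11 (assuming one drop-out per group), we would have 80% power to show a significant" difference. The detectable difference in percent change is 2.95 points and the expected one about 4.83.

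No step-down test is planned for the primary outcome, although section 9.6 uses Holm's step-down method for the secondary outcomes. Section 9.1 lists a graded response among the secondary hypotheses: "Higher-dose NAC will show larger changes in all of the biological signatures listed above compared to lower-dose NAC".

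**The concern.** The plan moved from Bonferroni to Tukey to gain power and stopped one step short. Single-step Tukey holds every pair to the cut-off needed for the largest of three differences. With three groups that is stricter than necessary once one pair has been rejected, because the remaining pairs can then be tested at unadjusted 5% without raising family-wise error above 5%.

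What is at stake is power for two of the three pairwise tests, low dose versus placebo and high versus low, if the response rises with dose as section 9.1 expects. With 12 per group planned, a possible gain of 9 to 16 points on those tests deserves a wording change. It is an efficiency matter. Nothing in the planned test is wrong.

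**Working it through.** **Inputs.** From section 9.2: 12 per group planned, 11 analysed; significance level 0.0167; power 80%; detectable difference 2.95; expected difference about 4.83. From section 9.6: Tukey on three pairs, DSCF if skewed. Assumed, because not stated: the SD, the low-dose mean, and two-sided testing.

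**1. The plan's own figures.** 0.05/3 = 0.0167, as stated. The 80% cannot be checked independently without an SD, so the SD was back-solved:
- Two-sample t, 20 df: the standardised difference needed is 1.487, so SD = 2.95/1.487 = 1.98.
- Pooled variance, 30 df: SD = 2.04.
- Normal approximation: SD = 2.95 × √(11/2)/(2.394 + 0.842) = 2.14.

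The remark that Tukey is less conservative than Bonferroni is correct. At 30 df the critical |t| is 2.465 for Tukey (0.0196 per comparison) and 2.536 for Bonferroni. The unadjusted 5% value is 2.042.

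**2. Why a step-down is allowed.** If any two of the three pairwise nulls are true, all three means are equal. The only intersection hypothesis to test is therefore the global null. Closed testing rejects a pair if (i) the largest |t| exceeds 2.465 and (ii) that pair's own |t| exceeds 2.042. Any pair beyond 2.465 meets both conditions, so no Tukey rejection is lost.

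**3. Ceiling on the gain.** For one pair the gain cannot exceed P(2.042 < T < 2.465), where T is noncentral t on 30 df with noncentrality Δ/(SD × √(2/11)). The maximum is 16.0 points, at noncentrality 2.27 (15.9 with 12 per group). With SD 2.04 this is Δ = 2.27 × 2.04 × 0.426 = about 2.0 points. The bound is at least 9 points for Δ between about 1.0 and 2.9. At Δ = 4.83 the noncentrality is 4.83/(2.04 × 0.426) = about 5.6, where both cut-offs are almost always passed.

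**4. Simulated power, Tukey to step-down** (11 per group, SD 2.05, 200,000 trials per pattern):

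| Means placebo/low/high | Low vs placebo | High vs low |
|---|---|---|
| 0/2.415/4.83 | 61.9% to 76.1% | 61.9% to 76.3% |
| 0/2.95/4.83 | 81.1% to 90.4% | 39.0% to 54.8% |
| 0/3.22/4.83 | +6.5 points | +14.7 points |
| 0/4.83/4.83 | +0.1 point | true null, 2% to 5% |
| 0/0/4.83 | true null, 2% to 5% | +0.1 point |

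At 0/2.415/4.83, high versus placebo is 99.8% for both methods. With SD 2.0 the same pattern gives 64% to 78% for low versus placebo and for high versus low, and 36% to 58% for rejecting all three pairs.

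**5. Error rate, equal variances.** Under the global null the rate of any rejection is 4.95% for both methods; it is the same by construction, because the first step is Tukey's. With one arm different, the remaining true null is rejected 2.0% of the time by Tukey and 5.0% by the step-down.

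**6. Rank fallback.** DSCF against its own step-down (SD 2.12, normal errors, large-sample critical values, 40,000 trials) gave gains of 18.4 and 18.6 points at 0/2.415/4.83, and 14.5 and 17.6 at 0/2.95/4.83.

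**7. Choice of gate.** Only a range-based gate keeps every rejection. At 0/1.475/2.95, an F-test gate missed a Tukey rejection of high versus placebo in about 1.1% of trials. A Kruskal-Wallis gate missed some DSCF rejection in 1.1%.

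**8. Unequal variances.** At means 0/4.83/4.83 with a pooled SD, false high-versus-low rejections were 7.6% for the step-down and 3.5% for Tukey at SDs 2/3/3, and 8.1% and 3.7% at SDs 1.5/2.5/2.5. These SDs are illustrative.

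**The case against.** The strongest reply is that Tukey is valid, standard and prespecified, and that its decisions agree with simultaneous intervals. That agreement has value in a trial meant to supply variability information for a later confirmatory study. Five points follow.

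- **Dose selection.** A reader might infer that the stricter cut-off puts dose selection at risk. It does not. Section 1.1 picks the superior dose by the larger rise in GSH, subject to a limit on dose reductions and discontinuations for adverse effects. Section 9.6 bases next steps on effect sizes. Neither rule uses a pairwise test. This objection stands in full.
- **Primary hypothesis.** Section 9.1 words it as high and/or low dose. The chance of at least one rejection is identical under both methods, and high versus low is listed there as a secondary hypothesis. This also stands.
- **Size.** A reader might put the loss at 18 points. Against Tukey that is impossible at this sample size, since 16.0 is the ceiling; about 18 appears only against DSCF. The gain also depends on an assumed graded response.
- **Robustness.** Tukey's unused error allowance protects against a false dose-versus-dose claim when group variances differ. Section 9.2 itself makes power conditional on the variability matching that of healthy controls. This is a real cost, although the SDs that show it are assumed.
- **Intervals.** Step-down decisions and simultaneous intervals may disagree. This stands as a cost.

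What survives is the dominance result. Under equal variances the range-based step-down never rejects less than Tukey and can reject more, and power is the plan's own reason for choosing Tukey.

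**Conclusion.** This is a cheap improvement and not an error in the plan. Under an assumed SD of about 2.0, 11 per group, two-sided tests, equal variances and a graded dose response, the step-down adds about 9 to 16 points over Tukey for low versus placebo and high versus low. The gain on low versus placebo falls to 6.5 points when the low dose reaches two thirds of the high-dose effect (3.22/4.83). Against DSCF it reaches about 18 points. It is about zero if the doses are equal or the low dose is inert, and there is none for high versus placebo at the expected effect.

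A reader might infer that the trial is underpowered, or that its error control is faulty. The documents support neither: family-wise error is controlled as planned, and section 9.6 is right that Tukey is less conservative than Bonferroni. Because the SD and the low-dose effect are not given, the range is conditional and should not be quoted as a fixed loss.

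**What to change.** Amend section 9.6 before unblinding:

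1. **Primary test.** If the largest pairwise |t| exceeds the three-group Tukey critical value, reject that pair and test each remaining pair at unadjusted two-sided 5%. If it does not, reject none.
2. **Skewed data.** Gate on the largest DSCF statistic, not on Kruskal-Wallis, then test the remaining pairs by pairwise Wilcoxon at unadjusted two-sided 5%. Use the same standardised Wilcoxon statistic in both steps, so that no DSCF rejection is lost.
3. **Unequal variances.** Use pair-specific (Welch) variances in the follow-on tests if group SDs clearly differ, and define in advance what counts as a clear difference. Where Welch applies, the guarantee of keeping every Tukey rejection no longer holds strictly.
4. **Estimation.** Keep Tukey simultaneous intervals, and state that a step-down rejection may accompany an interval that includes zero.

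The cost is SAP wording only, with no added participants, visits or data. The sample size in section 9.2 can stay. The price is the possible mismatch between decisions and intervals, and the loss of Tukey's spare error margin, which item 3 is meant to limit.
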